#### **9.4.5 Multiple Comparisons / Multiplicity**

To control the overall Type I error rate associated with multiple comparisons on the primary and key secondary endpoints at the 0.05 level (two-sided), the following hierarchical testing strategy will be employed:

- A. Conduct the statistical testing for the primary comparison between the tenapanor and placebo groups on the primary endpoint “change from baseline in s-P level at Week 4” at the significance level of 0.05 (two-sided).
- B. If the result of the primary comparison on the primary endpoint is positive (i.e., estimated mean difference  $<0$  and  $p$ -value  $\leq 0.05$ ), then conduct the statistical testing for the primary comparison between the tenapanor and placebo groups on the key secondary endpoint “s-P response at Week 4” at the significance level of 0.05 (two-sided).
- C. If the result of the primary comparison on “s-P response at Week 4” is positive (i.e., estimated rate difference  $>0$  and  $p$ -value  $\leq 0.05$ ), then conduct the statistical testing for the following two key secondary endpoints using the Hochberg step-up procedure to control the family-wise Type I error rate at the significance level of 0.05 (two-sided):
  - Relative change from baseline in iFGF23 at Week 4
  - Relative change from baseline in cFGF23 at Week 4

Analyses of other secondary endpoints will be descriptive. No multiplicity adjustment will be made for these analyses.

#### **9.4.6 Handling of Missing Data**

In the completed clinical study TEN-02-201 conducted by Ardelyx, the rate of missing s-P data was 6.25% (5/80) at both Week 2 and Week 4 visits during the 4-week Randomized Withdrawal Period. The rate of missing s-P data during the 4-week Double-Blind Treatment Period in the current study is expected to be in a similar range. The missing s-P data during the Double-Blind Treatment Period is expected to have limited impact on the study power and the accuracy of estimates for the current study.

The primary endpoint, change from baseline in s-P level at Week 4, will be analyzed using an MMRM on observed cases of the FAS. Changes from baseline in s-P level at Week 1, Week 2, and Week 3 will also be analyzed using the same MMRM on observed cases. To assess the impact of missing s-P data on the primary efficacy outcomes from the MMRM, sensitivity analyses such as ANCOVA using the last-observation-carried-forward (LOCF) imputation approach, completer analysis, and tipping-point analysis will be performed. Details of these sensitivity analyses will be provided in the SAP.

For other endpoints to be analyzed using ANOVA or ANCOVA and all binary response endpoints, missing data will be imputed using the LOCF approach after analysis.

Descriptive summaries of efficacy and safety measures will be based on observed data.

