## **9 STATISTICAL CONSIDERATIONS**

### **9.1 Statistical Analysis Plan**

A formal statistical analysis plan (SAP) will be provided separately. No changes are expected to the primary and secondary efficacy analyses. If the language in this protocol and the language in the SAP differ, the SAP governs. Results obtained from the analyses specified in the final approved version of the SAP will become the basis of the clinical study report for

this study. Any deviations from the final approved version of the SAP will be documented in the clinical study report.

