## **9.4 Statistical Methods**

### **9.4.1 General Considerations**

All measures will be summarized descriptively by treatment (planned or actually received). Descriptive statistics including the number of observations (n), mean, standard deviation, median, minimum, and maximum will be presented for continuous variables. Summary statistics for iFGF23 and cFGF23 will also include geometric mean and geometric coefficient of variation %. Frequency (n) and percent (%) will be presented for categorical variables.

Individual subject data including relevant derived variables will be listed.

Analyses of efficacy endpoints will be performed on the FAS and the PP population. The statistical testing will be conducted at a significance level of 0.05 (two-sided) unless specified otherwise. Analyses of safety measures will be performed on the Safety population. No statistical testing will be conducted for safety measures.

All data manipulations, descriptive summaries, and statistical hypothesis testing will be performed using SAS®.

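### LOCF is the only stated missing-data method for s-P response at Week 4, which gates FGF23 testing; for FGF23 and PTH it has only baseline to carry unless an early-termination sample exists, and early-termination values have no assignment rule

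*Combined protocol and SAP*

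**What the plan says.** **Missing data (Section 9.4.6).** The primary endpoint uses an MMRM on observed cases. For the remaining endpoints analysed by "ANOVA or ANCOVA and all binary response endpoints, missing data will be imputed using the LOCF approach after analysis". The named alternatives are LOCF ANCOVA, a completer analysis and a tipping-point analysis, and they have a stated purpose: "To assess the impact of missing s-P data on the primary efficacy outcomes from the MMRM, sensitivity analyses such as". Then: "Details of these sensitivity analyses will be provided in the SAP". The section closes by basing descriptive summaries on observed data. The expected missing rate comes from an earlier sponsor study, where "the rate of missing s-P data was 6.25% (5/80) at both Week 2 and Week 4 visits".

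**Testing order (Section 9.4.5).** Step A is the primary endpoint and step B is s-P response at Week 4. If step B is positive, "then conduct the statistical testing for the following two key secondary endpoints using the Hochberg step-up procedure", namely iFGF23 and cFGF23. PTH falls outside this chain: "Analyses of other secondary endpoints will be descriptive".

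**Sampling (Sections 1.3, 8.3, 8.5, 8.6; Table 8-1).** FGF23 and PTH are drawn twice, at Visit 4 and in the column shared by Visit 8 and ET. All Visit 8 evaluations are repeated at an ET visit, and Section 8.7 asks sites to obtain them at withdrawal.

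**Windows and populations.** Section 9.4.8 defines no analysis windows. It excludes data collected between scheduled visits except where they are used for imputation. Section 9.3 admits a subject to the FAS on one post-baseline s-P value, and to the Week 4 Completers on a Week 4 s-P assessment.

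**Governing document (Section 9.1).** "If the language in this protocol and the language in the SAP differ, the SAP governs". The separate SAP is not in the text supplied.

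**The concern.** There are three linked gaps.

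1. Step B decides whether FGF23 is formally tested at all. It has one missing-data rule, and nothing in the text supplied tests it under a different missing-data assumption.
2. A FAS subject must have a post-baseline s-P, but need not have a post-baseline FGF23 or PTH. Without a Visit 8 or ET sample, the last available value is baseline. Carrying it forces zero change for PTH. For FGF23 it gives a log-ratio of zero if the ratio is analysed. Under the literal definition (ratio minus 1 in Section 7.5, then log-transformed in Section 9.4.4) it gives log(0), which is undefined.
3. An ET value taken on, say, Day 10 can be read two ways. The shared Visit 8/ET column makes it a Week 4 observation and its subject a Week 4 Completer. Section 9.4.8 makes it off-schedule, usable only for imputation. Under LOCF both readings give the same carried value, provided the ET value is used to impute. In the primary MMRM on observed cases and in the Completers set they do not, so two programmers could build different Week 4 data sets.

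Separately, the LOCF sentence places imputation after the analysis. That order is impossible and looks clerical.

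**Working it through.** **Inputs.** From the protocol: 107 per arm, difference -0.5 mg/dL, SD 1.0, two-sided 0.05 (Section 9.2); missing rate 5/80 (Section 9.4.6). The documents give no response rates, FGF23 effect or split of missingness by arm, so those below are assumptions.

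**1. The plan's own figures.** Noncentral t, df = 212, noncentrality 0.5/√(2/107) = 3.66: power is 95.4% at 0.05 and 85.4% at 0.01, as stated. Missing: 107 × 0.0625 = 6.7 per arm; 214 × 0.0625 = 13.4. With about 100 per arm observed, power is 94.0% at 0.05 and 82.4% at 0.01. At 0.05, the protocol's claim of limited impact is fair for the primary endpoint.

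**2. Response: LOCF against non-response.** Suppose drop-outs' last values are below 5.5 mg/dL as often as in the rest of their arm. The gap between the two estimated differences is then m_T·r_T − m_P·r_P. Placebo is taken as 20%.

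| Tenapanor rate | Missing 6.25% / 6.25% | Missing 10% / 2.5% |
|---|---|---|
| 30% | 0.0625 × 0.10 = 0.6 points | 0.030 − 0.005 = 2.5 points |
| 40% | 0.0625 × 0.20 = 1.3 points | 0.040 − 0.005 = 3.5 points |
| 50% | 0.0625 × 0.30 = 1.9 points | 0.050 − 0.005 = 4.5 points |

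**3. Response: LOCF against multiple imputation.** Simulation, 1,000,000 per arm. Assumed: baseline mean 6.5 or 6.8 and SD 1.0, placebo change -0.2, change SD 1.0, between-visit correlation 0.5, Week 4 effect -0.5, drop-out equally likely after Week 1, 2 or 3 and either independent of or rising with Week 1 s-P, missing 6.25%/6.25% or 10%/2.5%. LOCF minus multiple imputation is +0.01 to -0.15 points if the effect is complete by Week 1. It is -0.25 to -0.66 points if the effect builds up evenly over four weeks.

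**4. Can the gate flip?** Constructed counts, Mantel-Haenszel with one stratum:
- 34/107 vs 21/107: z = 2.029, p = 0.042.
- With 2 and 1 carried responders recounted as non-responders, 32/107 vs 20/107: z = 1.908, p = 0.056.

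A second example uses observed rates of 40% and 25% and a pooled z-test:
- Missing split 10/3: non-response p = 0.053; LOCF with 35% to 60% of missing subjects carried as responders, p = 0.020 to 0.014; observed cases only, p = 0.021.
- Missing split 7/7: non-response p = 0.026; LOCF p = 0.028 to 0.031.

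**5. FGF23, if the ratio is analysed.** If 6.25% per arm carry baseline, the log-ratio difference is multiplied by 0.9375. An assumed true ratio of 0.80 becomes 0.80^0.9375 = 0.811, and 0.70 becomes 0.716. For a mean change small relative to the SD, the standardised effect is multiplied by 0.9375/√0.9375 = 0.968, as if 6.25% fewer subjects were analysed. This is an upper bound, because ET samples reduce the share affected.

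**6. ET values coded as Week 4.** If all 13.4 missing subjects had an ET value and the effect at ET were -0.25 or 0 mg/dL, the -0.5 difference would move by 0.0625 × 0.25 = 0.016 or 0.0625 × 0.5 = 0.031 mg/dL (3% or 6%).

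**7. Power cost of counting missing as non-response.** At 40% vs 20% with 107 per arm, power is 0.897. Multiplying both rates by 0.9375 gives 37.5% vs 18.75%, power 0.868.

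**The case against.** The best defence is that the protocol is not silent around these gaps.

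- "Analyses of efficacy endpoints will be performed on the FAS and the PP population". In addition, the Week 4 Completers are described generally as a sensitivity population, the list of sensitivity analyses is open-ended, and observed-data summaries would show whether LOCF moved the response rate. This partly stands. But a per-protocol repeat is not a missing-data analysis, neither population is linked to response, and a descriptive table is not a test of step B.
- A governing SAP may supply what is missing. This stands as a limit: the finding covers only the text supplied. However, the deferral in Section 9.4.6 concerns the sensitivity analyses for the primary outcome, and Section 9.1 expects no change to the secondary analyses.
- A reader might infer that LOCF can only ever carry baseline for FGF23 and PTH. The documents do not support that. A subject who attends an ET visit has a second sample, which Section 9.4.8 could allow into the imputation. The problem is confined to subjects without a Visit 8 or ET sample, and Section 8.7 should keep them few.
- The shrinkage in step 5 assumes that the ratio itself is log-transformed. Under the literal formula the subject has no analysable value. This stands, and the figures are conditional on that reading.

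**Conclusion.** The point holds and is minor. LOCF is the only stated missing-data method for the endpoint that gates FGF23, with no missing-data sensitivity analysis tied to it in the text supplied. For FGF23 and PTH it falls back on baseline when no Visit 8 or ET sample exists, and the status of an early ET value is open.

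At about 6.25% missing the consequences are small: 0.6 to 1.9 points of response against non-response with equal missingness, up to 4.5 points under the assumed uneven split, and at most 0.031 mg/dL on the primary difference. Only a borderline step B could change. The crossings of 0.05 shown above come from constructed counts or an assumed 10/3 split; the even split shows none.

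A reader might infer that LOCF was chosen to help tenapanor, or that it inflates the response difference. Neither is shown. In the simulation LOCF is level with or slightly below multiple imputation, and in the 10/3 example it lies close to the observed-case result while non-response is the outlier. Nor do the documents show that uneven drop-out will occur.

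**What to change.** 1. **s-P response.** Name at least one non-LOCF analysis for step B. Suitable choices are multiple imputation of s-P from the primary MMRM variables, dichotomised at <5.5 mg/dL and combined, and missing counted as non-response. Making multiple imputation the main analysis is optional.
2. **FGF23 and PTH.** Delete LOCF, analyse observed Week 4 values, and never carry baseline forward.
3. **ET samples.** State in one sentence that an ET sample counts as Week 4, and its subject as a Week 4 Completer, only if taken within Day 29 ± 2, and that an earlier ET s-P serves only as the last value in LOCF analyses.
4. **Clerical.** Correct the LOCF sentence so that imputation comes before analysis.

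The cost is protocol and SAP wording plus minor programming, with no new data. A few ET values leave Week 4. A subject whose only post-baseline s-P is an early ET value remains in the FAS but contributes only to LOCF analyses. The non-response analysis has slightly less power, about 87% against 90% at the assumed 40% vs 20%.

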#### **9.4.7 Adjustments for Covariates**

In general, the two randomization stratification factors (type of phosphate binder and s-P level at Visit 3) will be adjusted in inferential analyses of efficacy endpoints. Detailed information on covariate adjustment is provided in [Sections 9.4.3](#) and [9.4.4](#).

#### **9.4.8 Visit Windows**

No analysis visit windows will be formally defined. The schedule of assessments and procedures in [Section 1.3](#) details the intended collection of study variables at specified visits. Any additional data collected between scheduled visits will be included in subject data listings but will be excluded from statistical analyses, unless the additional data is used to impute missing data in the analysis.

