### 1.3 Schedule of Assessments and Procedures

	Screening	Run-in Period		Treatment Period				
	Visit 1	Visit 2	Visit 3	Visit 4	Visit 5	Visit 6	Visit 7	Visit 8/ET
	Week -4 to -3	Week -2	Week -1	Day 1	Week 1	Week 2	Week 3	Week 4
Visit Window	-30 to -14 d	-18 to -7 (5-16 days after V1)	-9 to -2 (5-9 days after V2)	1 e (2-9 days after V3)	8 ± 2	15 ± 2	22 ± 2	29 ± 2
Study Procedure								
Informed Consent	X							
Inclusion/ Exclusion Criteria	X			X f				
Demographics	X							
Medical/Surgical History	X			X g				
Prior/Con Meds	X	X	X	X	X	X	X	X
Physical Examination	X							X
Weight (pre-dialysis)	X							X
Height	X							
Vital Signs a	X			X				X
12-lead ECG	X							X
Safety Laboratory Evaluations b	X							X
Serum Phosphorus	X	X *	X	X	X	X	X	X
FSH Test c	X							
Pregnancy Test c	X							X
Randomization				X				
Study Medication Dispense and/or Return				X	X	X	X	X
FGF23 and PTH Blood Sample				X				X
Biomarker Blood Sample				X				X
AE Assessment		X	X	X	X	X	X	X

\* At Visit 2, a serum phosphorus level of <5.5 mg/dL or >10.0 mg/dL does not deem the subject ineligible. However, the subject may be discontinued at the Investigator's discretion.

a Vital signs include sitting or supine blood pressure and pulse, prior to dialysis.

b Safety laboratory evaluations will include the hematology and serum chemistry tests other than the serum phosphorus test listed in Table 7-1.

c FSH (postmenopausal females) and pregnancy tests are performed on all females <60 years of age unless there is a documented method of sterilization, or FSH test confirms post-menopausal status.

d Screening (Visit 1) could be 14 to 30 days (i.e. 2 to 4 weeks) before randomization following the short-interval schedule.

e Day 1 is the randomization day and serves as the reference day for all visits.

f Subjects must continue to meet all applicable inclusion/exclusion criteria before randomization, including the criteria based on the s-P level at Visit 3.

g Record only changes to medical history from Visit 1

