### **7.3.3 Electrocardiogram**

A 12-lead ECG will be performed after the subject has been in a sitting or supine position for at least 5 minutes.

The following ECG parameters will be recorded: heart rate, PR-interval, QRS-duration, QT-interval (uncorrected), QTc-interval (corrected), RR-interval and the Investigator's conclusion on the ECG profile.

The Investigator will assess whether the ECG is normal or abnormal; abnormal will be further subdivided into clinically significant and not clinically significant.

Electrocardiographic intervals and the Investigator's assessment of all abnormal ECGs will be recorded in the eCRF.

Additional ECGs may be obtained if clinically indicated.

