**7.3.5 Analysis of Clinical Laboratory Tests**

A certified laboratory will be used to process and provide results for the clinical laboratory tests. The baseline laboratory test results for clinical assessment for a particular test will be defined as the last measurement prior to the initial dose of study medication.

For any laboratory test value outside the reference range that the Investigator considers clinically significant, the Investigator will:

- Repeat the test to verify the out-of-range value.
- Follow the out-of-range value to a satisfactory clinical resolution.

Record as an AE any laboratory test value that (1) is confirmed and the Investigator considers clinically significant, or (2) that requires a subject to be discontinued from the study, or (3) that requires a subject to receive non-study treatment, or (4) fulfills one or more criteria for serious adverse event (SAE).

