#### **7.4.4 Following Adverse Events**

All (both serious and non-serious) AEs must be followed until they are resolved or stabilized, or until all attempts to determine resolution of the event are exhausted. The Investigator should use his/her discretion in ordering additional tests as necessary to monitor the resolution of such AEs.

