**Table 8-1: Approximate Blood Volume per Subject**

Test	No. of Samples	Volume Collected for Each Sample (mL)	Total (mL)
Chemistry + b-HCG+ FSH	2	7	14
Hematology (blood)	2	3	6
Phosphorus (serum)	8	4	32
PTH (plasma)	2	4	8
iFGF-23 (plasma)	2	4	8
cFGF-23 (plasma)	2	4	8
Serum biomarkers	2	5	10
Plasma biomarkers	2	6	12
Total	--	--	98

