#### **9.4.9 Safety Analyses**

Safety analyses include summaries for AEs, safety laboratory tests, vital signs, body weight, 12-lead ECG, and physical examination.

All AEs will be coded using the Medical Dictionary for Regulatory Activities (MedDRA). Treatment-emergent adverse events (TEAEs) will be tabulated by MedDRA system organ class and preferred term. Listings will also be provided for TEAEs.

Other safety measures will be summarized descriptively by treatment and visit.

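### The exclusion of between-visit data in Section 9.4.8 is not limited to efficacy, so on-treatment safety values taken between visits may reach listings only, and the rule can clash with the laboratory baseline in Section 7.3.5

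*Combined protocol and SAP*

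**What the plan says.** Section 9.4.8 defines no analysis visit windows and then gives a general rule: "Any additional data collected between scheduled visits will be included in subject data listings but will be excluded from statistical analyses". The sentence closes with a single exception, for imputation: "unless the additional data is used to impute missing data in the analysis". It does not mention efficacy or safety.

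Section 9.4.9 tabulates treatment-emergent adverse events by system organ class and preferred term. For everything else it says: "Other safety measures will be summarized descriptively by treatment and visit". The protocol describes no table of worst values, values at any time after dosing, or shifts from baseline.

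The protocol provides for unscheduled safety tests in three places. Section 7.3.5 asks for repeats and follow-up of clinically significant out-of-range laboratory values. Section 7.4.4 says the investigator "should use his/her discretion in ordering additional tests as necessary to monitor the resolution of such AEs". Section 7.3.3 says: "Additional ECGs may be obtained if clinically indicated".

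Section 7.3.5 also says that the baseline laboratory result "will be defined as the last measurement prior to the initial dose of study medication". Section 9.1 refers to a separate SAP that governs where it differs from the protocol. That SAP was not among the documents reviewed.

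**The concern.** Unscheduled safety tests are usually taken because something looks wrong, so they are more likely than routine samples to show an abnormality. A rule that keeps them out of analyses suits an efficacy endpoint measured at fixed visits. Applied to safety data, it leaves out the values most likely to be informative.

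Section 2.4 names electrolyte disturbances, metabolic acidosis, diarrhea and reduced blood pressure as theoretical risks in this population. An electrolyte or bicarbonate change could arise and resolve within four weeks. If it were seen on a draw between visits and had resolved by Visit 8, the by-visit laboratory table would not show it. A reader of the summary tables would see the Visit 8/ET values and nothing from the weeks before.

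The baseline is a second, smaller problem. Two sections give different answers on whether an unscheduled pre-dose result may be used.

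**Working it through.** **1. Inputs.** The visit schedule is in Section 1.3, the analytes in Table 7-1, and the sample counts and volumes in Table 8-1. The footnote to Section 1.3 defines the panel: "Safety laboratory evaluations will include the hematology and serum chemistry tests other than the serum phosphorus test listed in Table 7-1".

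**2. Reproducing the plan's own counts.**
- Safety laboratory visits in Section 1.3: Visit 1 and Visit 8/ET = 2. Table 8-1, row "Chemistry + b-HCG+ FSH", gives 2 samples, and the hematology row also gives 2.
- Serum phosphorus visits in Section 1.3: Visits 1 to 8 = 8. Table 8-1 gives 8.
- Total volume: 14 + 6 + 32 + 8 + 8 + 8 + 10 + 12 = 98 mL. Table 8-1 gives 98.

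The schedule and the blood-volume table agree.

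**3. Scheduled safety measurements strictly between Visit 4 (first dispensing) and Visit 8/ET.**

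| Measure | Scheduled at (Section 1.3) | Number at Visits 5 to 7 |
|---|---|---|
| Serum phosphorus | Visits 1 to 8 | 3 |
| Other chemistry | Visits 1, 8/ET | 0 |
| Hematology | Visits 1, 8/ET | 0 |
| 12-lead ECG | Visits 1, 8/ET | 0 |
| Vital signs | Visits 1, 4, 8/ET | 0 |

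Table 7-1 lists 16 chemistry analytes including phosphorus, and 16 − 1 = 15. For those 15, which include bicarbonate, potassium and sodium, every on-treatment value before Visit 8/ET is unscheduled. Section 7.3.2 says vital signs are taken at all visits, which differs from Section 1.3. If Section 7.3.2 is followed, the point is weaker for vital signs.

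**4. Where an unscheduled value goes under Sections 9.4.8, 9.4.9 and 7.3.5 as written.**

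| Value | By-visit table | AE table | Listing |
|---|---|---|---|
| Between visits on treatment, meets a 7.3.5 AE criterion | No | Yes | Yes |
| Between visits on treatment, meets none | No | No | Yes |
| Extra panel drawn at Visit 5, 6 or 7 | Not stated | Only if a criterion is met | Not stated |
| Repeat after an abnormal Visit 8/ET result | Visit 8/ET result stays in the table | Only if a criterion is met | Not stated |

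The second row is the gap. The imputation exception does not close it, because Section 9.4.6 bases safety summaries on observed data and no imputation of safety values is described.

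**5. Does the rule reach descriptive safety tables?** The synopsis places the safety summaries under its heading for statistical analyses. Section 9.4.1 plans analyses of safety measures but no testing of them, and Section 9.4.8 excludes data from analyses, not from testing. Section 9.4.8 also sets listings against analyses, and a summary table is not a listing. The broader reading is the more natural one. On the narrower reading, a between-visit value still has no stated place, because tables are by visit and no windows are defined.

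**6. Baseline.** The only scheduled pre-dose panel is Visit 1, 14 to 30 days before randomization. Suppose an out-of-range Visit 1 result is repeated between run-in visits. Section 7.3.5 makes the repeat the baseline, while Section 9.4.8 keeps it out of analyses. A change or shift from baseline would have to break one of the two rules.

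**The case against.** The strongest reply is that abnormalities that matter already have a route into tables. Section 7.3.5 requires an adverse event record when a value is confirmed and judged clinically significant, leads to discontinuation, needs non-study treatment, or is serious. Those events are tabulated whatever the visit. This stands, and it limits the gap to values that meet none of the four criteria. It does not remove the gap. A transient value that is normal on repeat may fail the first criterion, and an adverse event count does not show the size of a laboratory change.

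A second reply is that few such values may exist. Repeats of scheduled panels fall mainly in run-in or after Visit 8. Tests under Section 7.4.4 follow an adverse event that is already recorded. This also stands: what remains is ad hoc testing, and the documents give no expected frequency. However, the tabulated event need not be the laboratory finding. A test ordered during diarrhea may show a bicarbonate change that the diarrhea entry does not convey.

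Third, Section 9.4.6 speaks of descriptive summaries of observed data and Section 9.4.1 plans no safety testing, so the exclusion may not have been meant for safety tables. That is a fair reading, and it supports asking for clarification.

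Fourth, pooling unscheduled values can bias the comparison, because the arm with more GI events may be tested more often. This is correct and shapes the fix. Extra tables also cannot supply values that were never drawn.

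Finally, the baseline point is narrow. Section 7.3.5 gives its definition for clinical assessment, and a specific definition could be taken to override a general rule. The protocol gives no other baseline for safety laboratory tests, so one clause is still needed.

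**Conclusion.** The concern holds in a limited form. As written, Section 9.4.8 does not separate safety from efficacy. With by-visit tables only, between-visit on-treatment values for 15 of 16 chemistry analytes, and likewise for hematology and ECG, would appear in listings alone unless they meet an adverse event criterion. The number of values affected cannot be estimated from the documents. The baseline conflict arises only when the last pre-dose result is an unscheduled repeat and a change or shift from baseline is reported.

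A reader might infer more than this, and the documents do not support it:
- That all mid-treatment chemistry is lost. Phosphorus is scheduled at Visits 5, 6 and 7, and an extra panel drawn at one of those visits is not clearly excluded.
- That abnormal values vanish. They stay in listings, and those meeting Section 7.3.5 enter the adverse event tables.
- That the safety conclusion is biased toward no effect. That would need a rate of abnormal values outside the adverse event route, and none is given.

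The conclusion assumes that the term statistical analyses in Section 9.4.8 includes descriptive safety summaries, and that the separate SAP does not already provide otherwise. The primary analysis, its error rate and the sample size are unaffected. This is a worthwhile, low-cost improvement to the safety reporting.

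**What to change.** First check the separate SAP. If it already covers these points, align Section 9.4.8 with it. If not:

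1. State in Section 9.4.8 that the exclusion applies to efficacy analyses and by-visit summaries only.
2. For laboratory tests, vital signs and ECG, add a table by arm of the worst post-dose value and the shift from baseline, using scheduled and unscheduled values together. Define worst (low, high or both) for each measure in advance.
3. Keep the scheduled-only by-visit tables alongside, so that a difference caused by uneven testing can be recognised. Giving the number of unscheduled tests per arm would help the reader judge this.
4. State that the Section 7.3.5 baseline may be an unscheduled pre-dose value and that it is the baseline for safety change and shift tables.

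The cost is a few sentences and a small set of tables. Section 9.4.8 already requires the unscheduled values to be listed, so no new data collection is involved. The drawback is that the arm with more GI events may be tested more often, which item 3 makes visible but does not remove.
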